**Today's Date:**

08/7/2019

### FOR VA STUDIES

Has this application been approved by the ISO and Privacy Officer?

Yes - Please attach a copy of their approval with signature page.  
 No - **Do not submit application to IRB until approval has been received.**

### Section 1: General Questions

1. Do you or any of the investigators have a potential conflict of interest associated with this study?  
 Yes: Fill out and attach a [Disclosure Form B \(Disclosure of Financial Interests\)](#)  
 No
2. Is this study externally funded? (If yes, please attach a copy for each one selected)  
 No  
 Federally Sponsored Project-pending  
 Industry Sponsored Study  
 State Sponsored Project
3. If this project is for a student to complete their thesis or dissertation, has it been approved by the dissertation or thesis committee?  
 N/A  
 Yes  
 No **DO NOT submit an application until approval is granted**

4. Have you, or do you, plan to submit this study to another IRB?
 

Yes – please submit a copy of the IRB decision and approved consent/assent.  
 No
5. What is the purpose of your research? The purpose of this study are to develop and evaluate the feasibility and effectiveness of the Mobile Web App Breast Cancer Screening (wMammogram) intervention that is culturally tailored for American Indian (AI) women.
6. From the beginning, being the initial contact of participant(s) through last contact with participant(s) please describe the task(s) they will be expected to perform. (How will you contact them? What will you have them do?) The proposed study addresses two specific aims with a multi-method, two-phase research project that will take place in South Dakota over a three-year period. The two phases are: (1) developing the wMammogram intervention (Aim 1) and (2) evaluating the feasibility and efficacy of the wMammogram (Aim 2). Phase 1 incorporates a Community Based Participatory Research (CBPR) approach and a series of focus groups with various stakeholders in AI communities to design a culturally informed and practically refined intervention. Phase 2 uses a randomized clinical trial (RCT) design with AI women. In phase one, after the approval of the Yankton Tribal Institutional Review Board (IRB), [name] will convene two focus groups ( $N=20$ ;  $n=10$  for each group). Each group will consist of AI community leaders/members and local health professionals with backgrounds in cancer and health management. The purpose of the two focus groups will be to obtain firsthand information about the general public/health care professionals' beliefs, attitudes, and values about breast cancer and screening, as well as barriers, motivators, and possible triggers for screening. In phase two, the wMammogram intervention will be implemented with AI women using the blinded RCT over a seven-day period. Assessments with a mixed methods approach will be conducted at three intervals: baseline, one-week post-intervention, six-month follow-up survey, and post-intervention focus group.
7. Have you attached letters of approval from any schools or businesses involved?
 

Yes       N/A

Section 2: Participants

8. Please state the maximum number of participants you plan on enrolling. **107**
9. Please describe the study populations by checking all that apply.
 

 Males	 Females	 University Students
 Non-English Speaking	 Students in Grades K-12	
10. Are you **specifically** targeting an ethnic group? Check any that apply.
 

 American Indian	 African American	 Caucasian
 Alaskan Native	 Asian	 Pacific Islander
 Hispanic	 Other	
11. Age ranges of subjects to be enrolled?
 

 Birth-3	 Preschool 3-5	 Elementary 5-10
 Middle School 10-13	 High School 14-17	 Adult 18 and 64
 Senior Citizens 64 and up		
12. Please state any inclusionary and exclusionary criteria and how will the participants be screened.  Eligibility criteria include those: (1) who are self-identified AI women, (2) who are aged 40 to 70 years, (3) who have not received a mammogram in the past two years, (4) who live in South Dakota, (5) who are willing to possess an active email account, and (6) who are willing to use their own mobile phone or a mobile phone borrowed from the research team for the wMammogram intervention. The participant age range of 40-70 was selected based on the breast cancer screening guidelines of the American Cancer Society (ACS) that recommend women to begin regular mammograms at age 40. The exclusion criteria include those who (1) are minors (under 18 years), (2) received a mammogram in the past year, and (3) are under 40 or over 70 years of age.
13. Are any of the vulnerable populations listed below going to be enrolled in this study?

- Your employees
- Your students
- Prisoners
- Children
- Individuals with diminished mental/physical capacity
- Pregnant women
- Economically/educationally disadvantaged persons

14. Are the research participants your students or employees?

No

Yes – explain how you plan on avoiding your student(s) feeling or perceiving undue influence for participation

15. Where will the research take place? Yankton Sioux Tribe

16. If this research is taking place in a classroom, describe what non-participants will do during the research (activities and supervisions). Students not participating in the research should not be singled out or penalized. N/A

17. Will the participant(s) receive any compensation or extra credit? If so please describe what type (i.e. SONA extra credit, gift card, monetary). *If you are offering extra credit, please describe the non-research alternative way to earn the extra points. Please be sure to state this in the consent form along with a statement that students may stop participating at any time without losing the extra credit. To encourage participation, participants will be offered \$20 cash as an honorarium at three intervals (total \$60) : baseline, one-week post-intervention, six-month follow-up survey, and \$50 for initial development of web mammogram focus group and post-intervention focus group.*

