### Section 3: Recruitment

18. How do you have access to the study population? In collaboration with the Community Advisory Board, participants will be recruited through flyers, newspapers, radio announcements, social service agencies, ethnic community organizations, colleges, and ethnic events. Flyers and announcements will describe the purpose of the project, eligibility criteria, and contact information. Interested AI women will call the telephone number provided, and recruitment staff will screen potential participants over the phone to determine whether they meet the inclusion criteria.

19. Are you obtaining subjects from private records (i.e. through your job, volunteer work, internship, etc.)? The data could be consider private records unless it is publicly available to anyone.

Yes: Describe how you have permissible access.

No

20. How will you initially contact and select the participants? (i.e. letter, e-mail, or advertisement). *You must include all recruitment, announcements, and invites with your IRB application. Make sure they include the word "research", your study purpose, estimated time commitment, eligibility criteria, and your contact information for questions* Participants will be recruited through flyers, newspapers, radio announcements, social service agencies, ethnic community organizations, colleges, and ethnic events. Flyers and announcements will describe the purpose of the project, eligibility criteria, and contact information. Interested AI women will call the telephone number provided, and recruitment staff will screen potential participants over the phone to determine whether they meet the inclusion criteria.

21. Describe how the subject's privacy will be protected? (i.e. testing or interviewing in private) *Privacy is about the person NOT the data...think about where the procedures will be conducted.* Participants will conduct a survey in a private conference.

22. Will there be a link to identify subjects? *This could be a name, code, or reference that might be used to identify the subject outside of the context of the research setting. The key question is, "Is there any way that anyone, including the investigator, could start with a data record and trace it back to the person being studied?" If yes, then there is an identifier linked to the subject.*

Yes: Explain the link and justify its use.

No – Skip to question 25 below

23. Who will have access to the identifiers and who will keep the link?

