**Most exempt studies require a participant to be given a consent statement or a cover letter.**

27. Check (✓) all that apply. Prepare and attach forms/scripts for review.

Parental Consent (If the research is on a minor, parental consent is required. If minors are over 12 they can also sign the parental consent if it is written at a low literacy level.)  
 Informed Consent (Adults)  
 Assent Written (If child is ages 7-11 a written assent or verbal assent is required. Verbal assent requires a script.)  
 Assent-written within parental consent  
 Assent-verbal, script needed  
 Consent Statement (This can only be used on adults when no identifiers are collected.)  
 Cover Letter (This is similar to the consent statement but is in letter format.)

Templates can be found at <http://www.usd.edu/research/irb-application-forms>. Please utilize the templates to ensure regulatory compliance and avoid delays in processing this application.

28. If you will be using a consent statement or cover letter how will you obtain the consent?

Mailed to the subject  Verbal/Handout (face to face)  
 Web-based  Verbal (telephone)

29. Describe what will be said to the participant to introduce the research. If your study is a telephone survey or interview, you must include a telephone script. You are invited to participate in a research study. The purpose of this study is to develop and evaluate the feasibility and effectiveness of the Mobile Web App Breast Cancer Screening (wMammogram) intervention that is culturally tailored for AI women. In order to participate, you must be 40 or older AI women. Taking part in this research project is voluntary. Please take time to read this flyer and ask questions before deciding whether to take part in this research project.

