IRB CODE NUMBER: 2019.053
NCT number: 05530603

University of South Dakota

Department of Social Work

**Intervention To Promote Breast Cancer Screening Among
American Indian Women**

Statistical Analysis

Date of Document: 09/24/2019

Statistical Analysis: Prior to our hypotheses tests, group equivalence in terms of baseline characteristics will be examined using t-tests and chi-square tests. For Hypothesis 1, investigators will compare the percentage of women from each condition who receive mammograms or have scheduled a mammography appointment using a chi-square test. Investigators will supplement this with logistic regression analyses to adjust for confounding covariates. For Hypothesis 2, the averages of score change (pre- to post-test) from the two conditions will be compared using the two-sample t-test, and/or the Wilcoxon rank-sum tests after assessing normality of the scores. The group difference in terms of changes in the given constructs will be tested by a mixed-effect analysis of variance (ANOVA). The mixed-effect ANOVA includes both within-subject (i.e., time: repeated measures) and between-subject factors (i.e., group: intervention versus control) and aims to examine whether there is an interaction between these two factors on the dependent variable. Bonferroni correction will be used to reduce the probability of Type 1 error for multiple comparisons. Investigators will supplement this with a regression analysis of score change in order to adjust for confounding covariates. For Hypothesis 3, averages of general satisfaction and effectiveness scores from each group will be compared using the two-sample t-test. Also, the percentage of participants from each group who endorse "yes" for the intention and recommendation items will be compared using the chi-square test. To minimize a potential non-participation bias, investigators will closely monitor and compare the first and fourth quartiles of responses for differences in background variables and key constructs. Investigators will also carefully document the response rate over the course of this project. IBM SPSS version 25 will be used for data analyses.

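### Does the one-year mammogram exclusion conflict with the two-year inclusion window and change who is enrolled?

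*Protocol*

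**What the plan says.** Section 2, item 12 of the Protocol gives six inclusion criteria and three exclusion criteria in one paragraph. Two subjects appear in both lists.

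- **Mammogram history.** Inclusion: "3) who have not received a mammogram in the past two years". Exclusion: "2) received a mammogram in the past year".
- **Age.** Inclusion: "2) who are aged 40 to 70 years". Exclusion: "3) are under 40 or over 70 years of age". A separate exclusion line removes minors, defined as under 18.

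Section 3, items 18 and 20, both state that "recruitment staff will screen potential participants over the phone to determine whether they meet the inclusion criteria". The same items say of the recruitment materials: "Flyers and announcements will describe the purpose of the project, eligibility criteria, and contact information". The spoken introduction in item 29 tells women only this about eligibility: "In order to participate, you must be 40 or older AI women".

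For Hypothesis 1 the SAP compares the percentage of women in each group "who receive mammograms or have scheduled a mammography appointment using a chi-square test", supplemented by logistic regression. Neither document restates or explains either mammogram window anywhere else.

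**The concern.** The complement of the two-year inclusion is a mammogram at any time in the last 24 months. The exclusion covers only the last 12. A woman screened, say, 18 months ago fails the inclusion criterion but is not named by the exclusion. In the same paragraph the age exclusion is the exact complement of the age inclusion, so it is natural to suspect that one of the two mammogram windows was mistyped.

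The variable also matters. Of the eligibility criteria, time since the last mammogram lies closest to the Hypothesis 1 outcome. If some staff or flyers worked from the one-year line, the trial would take in more recently screened women, and its result would describe a different population from the one in the inclusion list. Eligibility text tends to be copied into scripts and flyers, so a loose line can spread.

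**Working it through.** No sample-size or error-rate formula applies, and the plan gives no figure to reproduce. The check is whether the two lists can be applied together and, if so, whom they admit.

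**Mammogram history.** Let *t* be the months since the last mammogram, with women never screened counted as beyond 24.

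| Last mammogram | Meets the two-year inclusion? | Caught by the one-year exclusion? | Eligible? |
|---|---|---|---|
| *t* up to 12 | No | Yes | No |
| *t* over 12, up to 24 | No | No | No |
| *t* over 24, or never | Yes | No | Yes |

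Eligible women meet the inclusion and avoid the exclusion: {*t* > 24} ∩ {*t* > 12} = {*t* > 24}. That is the inclusion set itself. Deleting the exclusion line, or lengthening it to two years, leaves the set the same. The line is redundant and contradicts nothing.

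**Which list is applied.** Items 18 and 20 describe the telephone screen as a check on the inclusion criteria. That list holds the two-year window. Neither item describes a screen that uses the exclusion list alone.

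**Does the paragraph follow a mirroring rule?** The case for a mis-stated window rests on the age lines.

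- Of the six inclusion criteria, only age has an exact complement among the exclusions.
- Mammogram history has a partial one.
- The other four (American Indian identity, South Dakota residence, email account, mobile phone) have none.
- The exclusion of minors under 18 lies wholly inside the exclusion of women under 40, so the list already holds a second narrower line that removes nobody further.

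One exact match in six, beside another redundant line, is not a convention from which a typing error can be inferred.

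**Other places.** The introduction in item 29 leaves out residence, email, telephone and the upper age limit as well as mammogram history. It is a short invitation, and its silence on the window is uninformative. The flyers and the pre-test are named as attachments to the amendment forms but are not among the documents available, so they support neither side.

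**The case for a change.** The strongest argument for acting is that the two redundant lines differ in kind. The line on minors gives no competing threshold that a screener might apply to a borderline caller; one year against two does. A busy recruiter could take the exclusion list as the working rule and enrol a woman last screened 18 months ago. Aligning the lines would cost one sentence, and recording the date of the last mammogram would make any such enrolment visible.

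Part of this stands. The wording is untidy, the two windows do differ, and the documents do not say why. The step to a consequence does not stand. It needs staff to set aside the inclusion list, which is the list the Protocol tells them to check. Applying that list already means asking each caller about the past two years, so the exact date would guard only against an error that nothing in the text points to.

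Nor can a size be put on such an error. The documents give neither the share of women last screened 12 to 24 months ago nor any uptake by screening history, so even the direction of an effect on Hypothesis 1 would be a guess. The eligibility lists also make no distinction between the study groups, so the mismatch gives no reason to expect bias between them.

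**Conclusion.** The mismatch is real but has no consequence for the plan. Read together, the two lists define one population, women with no mammogram in the past two years, and the one-year line alters it by nobody. The effect on enrolment, on the Hypothesis 1 comparison and on error rates is zero.

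This rests on two assumptions: every inclusion criterion must be met, which is the ordinary meaning of such a list, and staff screen as Section 3 describes. It does not depend on which window the investigators would choose if they tidied the paragraph; that is theirs to decide. Bringing the two lines into agreement at some later revision would be harmless editing, but the validity of the analysis does not depend on it.

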### Section 3: Recruitment

18. How do you have access to the study population? In collaboration with the Community Advisory Board, participants will be recruited through flyers, newspapers, radio announcements, social service agencies, ethnic community organizations, colleges, and ethnic events. Flyers and announcements will describe the purpose of the project, eligibility criteria, and contact information. Interested AI women will call the telephone number provided, and recruitment staff will screen potential participants over the phone to determine whether they meet the inclusion criteria.

19. Are you obtaining subjects from private records (i.e. through your job, volunteer work, internship, etc.)? The data could be consider private records unless it is publicly available to anyone.

Yes: Describe how you have permissible access.

No

20. How will you initially contact and select the participants? (i.e. letter, e-mail, or advertisement). *You must include all recruitment, announcements, and invites with your IRB application. Make sure they include the word "research", your study purpose, estimated time commitment, eligibility criteria, and your contact information for questions* Participants will be recruited through flyers, newspapers, radio announcements, social service agencies, ethnic community organizations, colleges, and ethnic events. Flyers and announcements will describe the purpose of the project, eligibility criteria, and contact information. Interested AI women will call the telephone number provided, and recruitment staff will screen potential participants over the phone to determine whether they meet the inclusion criteria.

21. Describe how the subject's privacy will be protected? (i.e. testing or interviewing in private) *Privacy is about the person NOT the data...think about where the procedures will be conducted.* Participants will conduct a survey in a private conference.

22. Will there be a link to identify subjects? *This could be a name, code, or reference that might be used to identify the subject outside of the context of the research setting. The key question is, "Is there any way that anyone, including the investigator, could start with a data record and trace it back to the person being studied?" If yes, then there is an identifier linked to the subject.*

Yes: Explain the link and justify its use.

No – Skip to question 25 below

23. Who will have access to the identifiers and who will keep the link?

24. How will you limit access to the subject identifiers?

25. Describe the security plan for data including where it will be stored and how long, noting that you may not keep identifiable data indefinitely. All data obtained will be kept confidential in accordance with the provision of title 42 Code of Federal Regulations and HIPPA. All hard copy information will be kept in locked files, in locked rooms only accessible by [name]. All data collected during the study will be entered into an electronic data system by a unique ID code that will be assigned to each participant. Access to computer files will be only [name]. All data will be maintained in a computerized data system on a secured and firewall protected server. Hard copies of the focus group and interview transcripts, notes, and surveys will be kept in locked cabinets for 3 years in the USD Department of Social Work.

Results from the study will be provided in the aggregate to avoid identification of any individual participant. Results will not be shared when there are not sufficient cases to assure confidentiality or when characteristics clearly identify a particular participant. No reports will include any identifying information on participants and no participant-specific information will be released without written permission of the participant.

26. Do you agree to keep a copy of the de-identified data for 3 years after the study closure?

Yes  
 No

**Most exempt studies require a participant to be given a consent statement or a cover letter.**

27. Check (✓) all that apply. Prepare and attach forms/scripts for review.

Parental Consent (If the research is on a minor, parental consent is required. If minors are over 12 they can also sign the parental consent if it is written at a low literacy level.)  
 Informed Consent (Adults)  
 Assent Written (If child is ages 7-11 a written assent or verbal assent is required. Verbal assent requires a script.)  
 Assent-written within parental consent  
 Assent-verbal, script needed  
 Consent Statement (This can only be used on adults when no identifiers are collected.)  
 Cover Letter (This is similar to the consent statement but is in letter format.)

Templates can be found at <http://www.usd.edu/research/irb-application-forms>. Please utilize the templates to ensure regulatory compliance and avoid delays in processing this application.

28. If you will be using a consent statement or cover letter how will you obtain the consent?

Mailed to the subject  Verbal/Handout (face to face)  
 Web-based  Verbal (telephone)

29. Describe what will be said to the participant to introduce the research. If your study is a telephone survey or interview, you must include a telephone script. You are invited to participate in a research study. The purpose of this study is to develop and evaluate the feasibility and effectiveness of the Mobile Web App Breast Cancer Screening (wMammogram) intervention that is culturally tailored for AI women. In order to participate, you must be 40 or older AI women. Taking part in this research project is voluntary. Please take time to read this flyer and ask questions before deciding whether to take part in this research project.

